5.4

Do any of the research procedures pose a physical or clinically significant psychological risk to women who are or may be pregnant or to a fetus?

* **Yes**

5.4.1

List the research procedures that pose a risk to pregnant women or fetuses:

Exposure to radiation can lead to abnormal fetal development.

5.4.2

Describe the steps that will be taken to rule out pregnancy prior to exposing women of child-bearing potential to the research procedures that pose a risk to pregnant women or fetuses:

A urine pregnancy test will be performed on all women of child-bearing potential on the day of,

and prior to, the PET scanning procedures.

5.4.3 Describe the measures to prevent pregnancy, and their required duration of use, that will be discussed with women of child-bearing potential during and following exposure to research procedures:

1. Subjects will receive a blood pregnancy test at screening.
2. A urine pregnancy test will be performed on all women of child-bearing potential on the day of, and prior to, the PET scanning procedures.
3. In addition, all female subjects will be educated and instructed to use contraception two-weeks prior to undergoing any of the radiation related procedures. A confirmation of their use of protection is documented in the case report form.

[\[reviewer notes-\]](#)

5.5 Do any of the research procedures pose a potential risk of causing genetic mutations that could lead to birth defects?

- * Possibly or Definitely

5.5.1 List the research procedures that pose a potential risk of genetic mutations/birth defects:

Exposure to radiation can lead to abnormal fetal development.

5.5.2 Describe the measures to prevent pregnancy, and their required duration of use, in female subjects and female partners of male subjects during and following exposure to research procedures:

1. Subjects will receive a blood pregnancy test at screening.
2. A urine pregnancy test will be performed on all women of child-bearing potential on the day of, and prior to, the PET scanning procedures.
3. In addition, all female subjects will be educated and instructed to use contraception two-weeks prior to undergoing any of the radiation related procedures. A confirmation of their use of protection is documented in the case report form.

[\[reviewer notes-\]](#)

5.6 Are there any alternative procedures or courses of treatment which may be of benefit to the subject if they choose not to participate in this study?

- * Not applicable

If **Yes**, describe in detail:

[\[reviewer notes-\]](#)

5.7

Describe the specific endpoints (e.g., adverse reactions/events, failure to demonstrate effectiveness, disease progression) or other circumstances (e.g., subject's failure to follow study procedures) that will result in discontinuing a subject's participation?

* Describe below:

Subjects will be withdrawn from the study at their request or by the determination of the study physician. Reasons could include experiencing claustrophobia during the MRI or PET scan, or experiencing adverse effects from hydrocortisone, or [C-11]NOP-1A, failure of adherence to research protocol.

[\[reviewer notes-\]](#)

5.8

Will any individuals other than the investigators/research staff involved in the conduct of this research study and authorized representatives of the University Research Conduct and Compliance Office (RCCO) be permitted access to research data/documents (including medical record information) associated with the conduct of this research study?

* Yes

5.8.1

Identify the 'external' persons or entity who may have access to research data/documents and the purpose of this access:

Other research investigators interested in this topic may be provided access to the de-identified data for data pooling and replication of these data.

5.8.2

Will these 'external' persons or entity have access to identifiable research data/documents?

*

No; the research data/documents will be coded and subject identifiers removed prior to access by the external persons

If **Yes**, describe how they will protect the confidentiality of the research data:

5.9

Has or will a Federal Certificate of Confidentiality be obtained for this research study?

* No

5.10

Question has been moved to 5.17

5.11 **Question has been moved to 5.16**

[\[reviewer notes-\]](#)

5.12 **Does participation in this research study offer the potential for direct benefit to the research subjects?**

No - Describe the general benefits to society (e.g., increased knowledge; improved safety; better health; technological advancement) that may result from the conduct of this research study.

Describe the benefit:

The general benefits to society from this particular research protocol include gaining a better understanding of the effect of nociceptin-corticotrophin interactions. It is possible that future studies using this paradigm may detect that this interaction is abnormal in addictive and psychiatric disorders, and lead to better treatments.

5.13 **Describe the data and safety monitoring plan associated with this study. If the research study involves multiple sites, the plan must address both a local and central review process.**

The study results will be monitored on a bi-monthly basis to ensure appropriate data collection and study procedures justify the continuation of the study. The PI will ensure that the IRB, and when applicable (i.e., if felt to be related to administration of a radioactive drug) the RDRC, is immediately notified of any adverse event. [name] is routinely notified of any medical concerns during the conduct of the study. The PET methodology, including the arterial blood draw procedure, is reviewed at least monthly to ensure that risk is minimized and participant comfort maximized. Expected and unexpected serious (including fatal) adverse reactions and major unresolved disputes between the research investigator(s) and the research participant or between research investigator(s) will be expeditiously reported to the IRB and, when applicable (i.e., if felt to be related to administration of a radioactive drug) the RDRC as per Chapter 3, Section 3.3 of the IRB reference manual. At the time of renewal, the IRB will be provided with a summary indicating the frequency of the monitoring, cumulative adverse event data, information regarding participant safety or ethics changes, confidentiality issues, benefit-to-risk changes and recommendations on continuing, changing or terminating the study. None of the investigators have a conflict of interest with the radiotracer ([C-11]NOP-1A) or hydrocortisone being used in this study.

[\[reviewer notes-\]](#)

Section 5 - Potential Risks and Benefits of Study Participation

5.14 **What precautions will be used to ensure subject privacy is respected?** (e.g. the research intervention will be conducted in a private room; the collection of sensitive information about subjects is limited to the amount necessary to achieve the aims of the research, so that no unneeded sensitive information is being collected, drapes or other barriers will be used for subjects who are required to disrobe)

- 1) All research intervention will be conducted in a private room.
- 2) The collection of sensitive information about subjects is limited to the amount necessary to achieve the aims of the research, so that no unneeded sensitive information is being collected.
- 3) Drapes or other barriers will be used for subjects who are required to disrobe for procedures, such as EKG, etc.

5.15

What precautions will be used to maintain the confidentiality of identifiable information? (e.g., paper-based records will be kept in a secure location and only be accessible to personnel involved in the study, computer-based files will only be made available to personnel involved in the study through the use of access privileges and passwords, prior to access to any study-related information, personnel will be required to sign statements agreeing to protect the security and confidentiality of identifiable information, whenever feasible, identifiers will be removed from study-related information, precautions are in place to ensure the data is secure by using passwords and encryption, because the research involves web-based surveys, audio and/or video recordings of subjects will be transcribed and then destroyed to eliminate audible identification of subjects)

- 1) To minimize these risks, a study code number will be assigned and no subject will be identified by name. This will ensure subject confidentiality. The study code will be used to identify all data. The code containing the subject's name and number will be kept secure by the Study Investigator in a password protected electronic database behind UPMC firewall at PET Facility. All the investigator's research personnel will be allowed access to information on a need to know basis only.
- 2) All data collected will be kept in locked file cabinets in a locked and secured area.
- 3) All imaging data stored in electronic archives such as computers are de-identified, password protected and/or stored on the PET/MR imaging facility servers that are behind a UPMC Fire wall. Images that are acquired do not typically have any identifying data of the subjects entered. They are de-identified by the technician and assigned a code--the link between this code and imaging data files are maintained in a protected PET facility database.

5.16

If the subject withdraws from the study, describe what, if anything, will happen to the subject's research data or biological specimens.

If the subject withdraws from the study their clinical and imaging data will be de-identified. These de-identified data that was collected up until the time they withdrew consent may continued to be cited in analysis and/or publications with reasons for withdrawal of consent . Biological specimens such as blood samples that are stored for future analysis will be destroyed after the subject withdraws consent because there is no use for them unless the subject completes the entire imaging protocol.

5.17

Following the required data retention period, describe the procedures utilized to protect subject confidentiality. (e.g., destruction of research records; removal of identifiers; destruction of linkage code information; secured long-term retention)

All research records will be kept in locked, secured facilities for at least 7 years or until the investigators have completed analyzing and publishing the data, whichever occurs later. After that time, data will be secured for long-term retention (this will include PET and MRI images that will be archived in the PET Facility servers).

[\[reviewer notes-\]](#)

6.1 Will research subjects or their insurance providers be charged for any of the procedures (e.g., screening procedures, research procedures, follow-up procedures) performed for the purpose of this research study?

*

No

[\[reviewer notes-\]](#)

6.2 Will subjects be compensated in any way for their participation in this research study?

* Yes

6.2.1 Describe the amount of payment or other remuneration offered for complete participation in this research study.

Healthy Control Participants (HC) will be paid up to \$1100 for their participation in this protocol.

6.2.2 Describe the amount and term of payment or other remuneration that will be provided for partial completion of this research study.

Healthy Control Participants (payment breakdown for the total of \$1100)

- 1) One hundred dollars (\$100.00) will be paid for completing all listed screening procedures (SCID, psychiatric rating scales, physical exam, blood work);
- 2) Fifty dollars (\$50.00) will be paid for completion of the structural MRI scan;
- 3) One hundred dollars (\$100.00) for the arterial line;
- 4) Two hundred and fifty dollars (\$250.00) for completion of each [C-11]NOP-1A PET scan (\$250.00 x2 =\$500);
- 5) One hundred and fifty (\$150.00) for completion of the hydrocortisone challenge;

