1.1 Objective: What is the overall purpose of this research study? (Limit response to 1-2 sentences.)

To develop an imaging methodology to examine corticotropin-releasing factor (CRF)-nociceptin receptor (NOP) interactions in humans.

1.2 Specific Aims: List the goals of the proposed study (e.g., describe the relevant hypotheses or the specific problems or issues that will be addressed by the study).

Aim 1: To determine if [C-11]NOP-1A receptor binding (VT) can be altered by an intravenous hydrocortisone (cortisol) challenge through CRF-NOP interactions.

In rodents, an injection of CRF into the lateral cerebroventricle results in increased NOP receptor expression (Rodi et al., 2008). We will test the existence of such an interaction in 20 healthy human subjects by measuring [C-11]NOP-1A VT under control conditions and following the administration of intravenous cortisol (hydrocortisone, 1 mg/kg). Note: Intravenous CRH is not used as a challenge, because it is not transported from the blood to the brain (Martins et al., 1996). Intravenous hydrocortisone (1mg/kg) will be used as the challenge, because in vivo microdialysis studies in sheep have demonstrated that it can cross the blood-brain barrier and increase CRF levels in the amygdala by ~ 200% (Cook, 2002; Schwartz et al., 1972). Hydrocortisone increases amygdala CRF levels via its action on type 2 glucocorticoid receptors (Cook, 2002).

The hypothesis is that hydrocortisone-induced increases in amygdala CRF will result in higher [C-11]NOP-1A VT. This would suggest that transmission at NOP receptors is increased to counteract hydrocortisone's activation of CRF and the brain stress system. If successful, future studies will be proposed with this hydrocortisone- [C-11]NOP-1A PET imaging paradigm to examine CRF-NOP interactions in addictive disorders.

1.3 Background: Briefly describe previous findings or observations that provide the background leading to this proposal.

A1. Nociceptin: a functional CRF antagonist

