
A3. Imaging of NOP receptors with [C-11]NOP-1A and PET

In a major advancement, the imaging group at NIMH recently radiolabeled and successfully validated a NOP receptor antagonist radiotracer [C-11] (S)-3-(2'-fluoro-6',7'-dihydrospiro[piperidine-4,4'-thieno[3,2-c]pyran]-1-yl)-2-(2-fluorobenzyl)-N-methylpropanamide (NOP-1A) for use in humans (Pike et al., 2011). [C-11]NOP-1A binds with relatively high affinity to NOP receptors (KD, 0.15 nM). [C-11]NOP-1A total uptake in various brain regions (VT) is consistent with the known distribution of NOP receptors in human and primate brain (relatively

high density in amygdala, striatum and cerebral cortex; and moderate density in cerebellum and midbrain) (Berthele et al., 2003; Bridge et al., 2003; Kimura et al., 2011; Lohith et al., 2012). Blocking studies in primates with the specific NOP receptor antagonist SB-612111 (KD 0.33 nM, 1mg/kg intravenously) indicate that 50-70% of [C-11]NOP-1A VT in brain regions represents specific binding to NOP receptors (Kimura et al., 2011). [C-11]NOP-1A demonstrates desirable pharmacokinetics in humans: brain uptake peaks relatively quickly (~ 10 min) and washes out rapidly; brain data is modeled well by a 2-tissue compartment kinetic analysis; VT values in brain regions range from 7 to 15; VT remains stable following 70 min of data acquisition; and the test-retest variability for VT is an acceptable $\leq 15\%$ in all brain regions (Lohith et al., 2014; Lohith et al., 2012).

[C-11]NOP-1A has been administered to approximately 50 subjects at the University of Pittsburgh PET facility by the PI in his prior research studies. Subject populations that it has been administered to include healthy subjects, alcoholics, cocaine addicts and PTSD subjects. To date no adverse reactions have been reported with its use.

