A). Baseline review of medical and medication history (to document no change from screening).

B). A urine pregnancy test is done on females of child bearing potential (i.e., females who have not undergone a surgical sterilization procedure or who are not at least one year post-menopausal) to confirm that pregnancy has not occurred between the time of the screening and the PET. In addition, a statement of use of a method of contraception for all subjects in the past 15 days (abstinence, barrier methods, oral contraceptive medications, etc.) is obtained.

C). A urine drug screen and alcohol breath analyzer to ensure the subject did not abuse any illicit drugs or alcohol prior to the PET scan (this test will occur prior to the placement of the venous and arterial catheters). Subjects will be informed that this test will occur.

D). The preparation of the subject will include the placement of a venous line and an arterial line. An anesthesiologist will place the arterial line. The purpose of these lines is as follows:

Arterial line (all subjects):

1. Blood sampling for [C-11]NOP-1A arterial concentration.
2. The arterial line will be placed after completion of the Allen test and infiltration of the skin with 1 to 2% lidocaine.

If the arterial line cannot be obtained for any reason, the PET study will NOT proceed as an arterial input function is necessary for the derivation of the primary outcome measure, total distribution volume (VT). Note: As the radiotracer [C-11]NOP-1A does not have a reference region (i.e., region devoid of NOP-1A specific binding), it is necessary to have the arterial input for appropriate quantitation of NOP-1A binding (Kimura et al., 2011).

Venous line (all subjects):

1. [C-11]NOP-1A (single bolus).

E). Blood pressure, heart rate and temperature will be documented prior to the PET scan.

F). Before the PET and CT scan procedures are initiated, a wrist band (Empatica, E4) will be placed on the subject's wrist that does not have the arterial line. This wrist band which looks similar to 'apple watch' will continuously monitor and record the subjects' heart rate, inter-beat interval, and electrodermal activity. Subjects will wear this wrist band till the completion of both their PET/CT scans.

G). A low-dose CT scan to correct the PET scan measurements for attenuation will be performed in a few minutes.

H). Following this CT scan, 12 mCi of [C-11]NOP-1A will be injected intravenously. Dynamic PET data will be collected for 70 min.

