and drug use disorders. The only information documented is the relationship to the participant and that no names, date of birth or other identifiers will be documented.

2.16.2

If the information about the third party is of a private nature, can the identity of the third party be readily ascertained or associated with this information?

*

No

Describe the **private information** that will be collected and recorded about the third party: We simply intend to ask information from subjects---medical illness, mental illness and drug and alcohol use in first- and second-degree relatives---to determine items which would be exclusionary for the subject's participation in this study, or related to imaging outcome measures derived in the subject. This information will be no different than the family history obtained during a routine physical and psychiatric exam.

[\[reviewer notes-\]](#)

2.17 What are the main outcome variables that will be evaluated in this study?

The main outcome measure will be the change in [C-11]NOP-1A VT elicited by hydrocortisone-stimulated CRF (Δ VT). Δ VT will be calculated as the difference between VT measured in the post-hydrocortisone condition and VT measured in the baseline condition on that day (VT BASE), and expressed as a percentage of VT BASE.

2.18 Describe the statistical approaches that will be used to analyze the study data.

* Addressed below:

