In the study by Rodi et al., infusion of 1 μ g CRF in rodents was associated with a 100% increase in NOP mRNA (Rodi et al., 2008). Based on prior microdialysis studies, we postulate a 2.2-fold increase in amygdala CRF following the 1 mg/kg IV hydrocortisone challenge (Cook, 2002). This is physiologically meaningful because it is in line with increases in amygdala CRF (~1 to 4-fold increase) that have been reported in animal models of addiction (Merlo Pich et al., 1995; Richter et al., 1995; Richter and Weiss, 1999; Richter et al., 2000). However, the exact magnitude that this will translate to increased NOP receptor binding as measured by [C-11]NOP-1A is unknown. Assuming a relatively modest 10% increase in binding to NOP receptors (VT) in response to CRF released by the hydrocortisone challenge, and a 10 - 14% within-subject test-retest variability for [C-11]NOP-1A VT (Lohith et al., 2014), the study is powered at 0.96 to 0.76 to detect an effect at the $p < 0.05$ level using a two tailed paired t test with a sample size of $n = 16$. It is possible that some subjects may not tolerate the hydrocortisone infusion to complete the PET scans. Thus, we request permission to study an additional 4 subjects, for a total $n=20$. Note: If we observe an effect on [C-11]NOP-1A VT as reported in Rodi et al. (100% increase in NOP mRNA), the study will be powered at 1.0.

[\[reviewer notes-\]](#)

3.13 Inclusion Criteria: List the specific criteria for inclusion of potential subjects.

1) Males or females between 18 and 40 years old, of all ethnic and racial origins.

3.14 Exclusion Criteria: List the specific criteria for exclusion of potential subjects from participation.

(1) Current DSM-5 psychiatric disorders including tobacco, alcohol and substance use disorders; and no past history of treatment of DSM5 disorders (SCID screening modules).

(2) History of binge drinking as defined in NIAAA criteria in the past month (<http://www.niaaa.nih.gov/alcohol-health/>). NIAAA defines "binge drinking" as a pattern of drinking that brings blood alcohol concentration (BAC) levels to 0.08 g/dL. This typically occurs after 4 drinks for women and 5 drinks for men—in about 2 hours;

(3) Recreational abuse of opiates, sedative-hypnotics, cocaine, amphetamines, MDMA, and PCP, as well as cannabis use (urine drug screen on PET day, and screening day);

(4) Currently on any prescription medical or psychotropic medication;

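### Does section 3.12 overstate power by treating a 10% rise in NOP receptor binding as a 10% rise in VT?

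*Combined protocol and SAP*

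**What the plan says.** The sample-size argument in section 3.12 assumes "a relatively modest 10% increase in binding to NOP receptors (VT") after hydrocortisone. It pairs this with "a 10 - 14% within-subject test-retest variability for [C-11]NOP-1A VT" and concludes that "the study is powered at 0.96 to 0.76 to detect an effect" with a two-sided paired t-test at 0.05 and 16 subjects. Four more are requested to cover incomplete scans, making 20. A closing note adds that if the rodent result carried over ("100% increase in NOP mRNA), the study will be powered at 1.0").

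Three other places bear on the meaning of the 10%:

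- Section 1.3 (A3) reports from primate blocking studies that "50-70% of [C-11]NOP-1A VT in brain regions represents specific binding to NOP receptors".
- Section 2.6 (arterial line) describes VT as the total distribution volume and explains why arterial sampling is needed: "As the radiotracer [C-11]NOP-1A does not have a reference region".
- Section 2.17 makes the main outcome the change in VT from baseline ("VT BASE), and expressed as a percentage of VT BASE").

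The aim in section 1.2 is to learn whether tracer "receptor binding (VT) can be altered by an intravenous hydrocortisone (cortisol) challenge". There too, VT in brackets is attached to the phrase about receptor binding.

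**The concern.** VT is a total measure: a part bound to NOP receptors plus a part that is not. If hydrocortisone acts only on the receptor-bound part, the percentage change in VT is the percentage change in that part multiplied by its share of the total. Section 1.3 puts the share at 50-70%, and without a reference region the outcome cannot be reduced to the specific part. Section 3.12 speaks of binding to NOP receptors but applies no such factor.

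Taken as a receptor change, 10% becomes 5-7% in VT, and a study presented as well powered would not be. With 16 completers, a real 10% receptor rise would be missed in about 26% to 73% of such studies. Section 1.2 makes further work with this imaging paradigm conditional on success here, so a false negative could lead to a usable method being dropped.

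**Working it through.** **Inputs.** Section 3.12: two-sided alpha 0.05, paired t-test, n = 16 (15 degrees of freedom), effect 10%, variability 10% to 14%. Section 1.3: specific share of VT, f = 0.5 to 0.7 (primates).

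**Step 1: reproduce the stated power.** Take 10% and 14% as the SD of the paired percentage difference in VT. The noncentrality parameter is (effect / SD) × √n.

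- SD 10%: (10/10) × 4 = 4.00, exact power 0.962.
- SD 14%: (10/14) × 4 = 2.86, exact power 0.761.

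These match 0.96 and 0.76. A normal approximation gives 0.979 and 0.815, and a one-sided t-test gives 0.985 and 0.860. Treating 10-14% as a single-scan SD, and so multiplying by √2, gives 0.753 and 0.472. None of these matches the stated pair. The calculation behind section 3.12 therefore used a 10% change in VT and an SD of the paired difference of 10% to 14%.

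**Step 2: apply the alternative reading.** Change in VT = f × change in specific binding, if non-specific uptake stays fixed: 0.5 × 10% = 5% and 0.7 × 10% = 7%.

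| Rise in VT | Power, n = 16, SD 10% / 14% | Power, n = 20, SD 10% / 14% | n for 80% power, SD 10% / 14% |
|---|---|---|---|
| 10% | 0.96 / 0.76 | 0.99 / 0.86 | 10 / 18 |
| 7% | 0.74 / 0.46 | 0.84 / 0.56 | 19 / 34 |
| 5% | 0.46 / 0.27 | 0.56 / 0.33 | 34 / 64 |

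On this reading, 20 completers reach 80% power only with a 70% specific share and an SD of 10%.

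**Step 3: decide which reading the text supports.** The sentence in section 3.12 puts VT in brackets directly after the words about binding. Sections 1.2, 2.6 (study goal) and 2.18 use the same label for the tracer measure. The sentence just before it in section 3.12 speaks of binding as measured by the tracer. The variability in the same sentence is stated for VT, and the outcome in section 2.17 is percentage change in VT. Effect, SD and outcome are thus on one scale, and Step 1 shows that the authors calculated on it.

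**Step 4: what a 10% rise in VT implies for receptors.** Inverting Step 2: 10 / 0.7 = 14.3% and 10 / 0.5 = 20%. The protocol's rodent evidence is a rise of about 70% in receptor protein after restraint stress (section 1.3, A1) and 100% in mRNA after CRF (section 3.12). Passed through the same factor:

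- 70% becomes 0.5 × 70 = 35% to 0.7 × 70 = 49% in VT.
- 100% becomes 50% to 70% in VT.

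A 10% rise in VT lies well below both. The closing note is also unaffected: even a 50% rise in VT is far above the 10.5% that 16 subjects detect with 80% power at the larger SD.

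**The case for a change.** The best case for a change is that reading the 10% as VT leaves something unexplained. The rationale in section 3.12 is about receptors: it starts from rodent mRNA and moves to a change in tracer binding without a conversion, although the protocol itself supplies the factor. A reader who takes the stated assumption as a 10% receptor change will think the study can detect one, when the assumption amounts to 14-20%. The sentence also does not say that 10-14% is the SD of the paired difference.

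Part of this stands. Section 3.12 does not give the implied change in specific binding, and a null result from 16 subjects could not rule out a 10% rise in specific binding. The SD is identified only by reproducing the result.

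It does not carry further, for three reasons. First, section 3.12 openly says that the size of the effect on tracer binding is unknown and that the study will supply an effect size for a later, adequately powered one. The 10% is a declared working assumption, and one missed result need not end the programme. Second, the 50-70% comes from primates and the documents give no human value, so it cannot replace a stated assumption about human VT. Third, whether the cited test-retest study reported a different statistic cannot be settled from the documents, and the calculation is consistent with the SD reading.

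**Conclusion.** The concern does not hold as an error in the power calculation. For a 10% rise in VT, which is how section 3.12 labels its effect, power at n = 16 is 0.96 to 0.76 as stated. The range of 0.74 to 0.27 is correct arithmetic for a different assumption, a 10% rise in specific binding alone. It depends on three conditions: the VT label is disregarded, the primate share of 50-70% applies to humans, and hydrocortisone leaves non-specific uptake unchanged.

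What remains is loose wording that an informed reader can resolve. Under the last two conditions, the assumed 10% in VT corresponds to 14-20% in specific binding. That is modest beside the rodent figures the protocol relies on, although those figures do not establish the size in humans. Spelling this out would leave the sample size, the test, the outcome and the stated power as they are, so no change to the plan is needed. The conclusion takes the 10-14% as the SD of the paired percentage difference, which is the reading that reproduces the stated figures.
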